7.2 Preparation/Handling/Storage/Responsibility

not applicable

7.3 Measures to reduce bias:

not applicable

7.4 Follow-up and Compliance

3 months mRS Score: 0-2 indicates a good outcome, 4-6 indicates a poor outcome
Grading Description:

- 0: No symptoms at all

- 1: No significant disability despite symptoms; able to carry out all usual duties and activities
- 2: Slight disability; unable to carry out all previous activities but able to look after own affairs without assistance
- 3: Moderate disability; requiring some help but able to walk without assistance
- 4: Severe disability; unable to walk without assistance and unable to attend to own bodily needs without assistance
- 5: Very severe disability; bedridden, incontinent, and requiring constant nursing care and attention
- 6: Death

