5.3 Determining sample size

Assuming a 40% probability of poor prognosis at 3 months after AIS, with an OR of 2.0 for high KLK10 expression and a correlation coefficient of 0.5 between KLK10 and other influencing factors, a significance level of 0.05, and a test power of 0.8, the required sample size is calculated using PASS11 software's Logistic Regression module. A total of 182 AIS cases are needed. Additionally, 91 age- and gender-matched individuals will be selected as healthy controls in a 2:1 ratio.

6. Research subjects

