7.1.4 Items and frequency of clinical and laboratory examinations to be conducted

- 1) Collect reports of complete blood count and biochemical tests upon admission: including neutrophil and lymphocyte counts, blood glucose, creatinine, and high-sensitivity C-reactive protein levels.
- 2) Collect blood pressure information upon admission.
- 3) Collect reports of cranial MRI or CT scans upon admission, and record the Alberta Stroke Program Early CT Score (ASPECTS) (0-10 points).
- 4) Measure levels of neuroinflammatory markers KLK10, sTREM2, and GFAP in plasma at admission, and at 24 hours and 7 days after stroke
- 5) Assess the degree of neurological impairment using the National Institutes of Health Stroke Scale (NIHSS) at admission, and at 24 hours, 4 days, 7 days, and discharge after stroke.
- 6) Collect information on infarct volume within 7 days after stroke, measured using diffusion-weighted imaging (DWI) (J Neuroinflammation. 2020 Apr 7;17(1):107).
- 7) Collect information on brain edema grading within 7 days after stroke, measured using non-contrast cranial CT scans. The severity of brain edema in AIS patients is assessed with a score of 0-3 based on our established method (Clin Neurol Neurosurg. 2022 Nov 2;223:107507).
- 8) Collect information on hemorrhagic transformation within 7 days after stroke, measured using non-contrast cranial CT scans.
- 9) Record the Modified Rankin Scale (mRS) score at 3 months after stroke.

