8.3 Loss to follow-up

To reduce loss of follow-up and missing data, patients who were not followed up on time were contacted by telephone.

9. Study endpoint evaluation

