9.1 Primary Endpoint Evaluation

The study examines the association between plasma levels of KLK10, sTREM2, and GFAP with favorable functional outcomes at 3 months after stroke onset.

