10.2 Primary Endpoint Analysis

Investigate the association between plasma KLK10, sTREM2, and GFAP levels and functional prognosis at 3 months: Univariate and multivariate logistic regression models are used to evaluate independent predictors, and odds ratios (OR) with 95% confidence intervals (CI) are calculated. ROC curves are plotted and the area under the curve (AUC) is calculated.

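### The 3-month outcome rule leaves mRS 3 unassigned, so the primary binary outcome is not defined for those patients

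*Combined protocol and SAP*

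**What the plan says.** All references are to the combined protocol and SAP.

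- **Section 7.4** gives the outcome rule: "3 months mRS Score: 0-2 indicates a good outcome, 4-6 indicates a poor outcome". The grading list below it includes "3: Moderate disability; requiring some help but able to walk without assistance", and attaches no outcome class to that grade.
- **Section 9.1** sets the primary endpoint as the association of the three plasma markers with "favorable functional outcomes at 3 months after stroke onset", without a cut-off.
- **Section 10.2** analyses "functional prognosis at 3 months: Univariate and multivariate logistic regression models are used to evaluate independent predictors", with odds ratios, ROC curves and AUC. That reads as a binary outcome; again no cut-off is given.
- **Section 5.3** sizes the study by "Assuming a 40% probability of poor prognosis at 3 months after AIS" and does not say which grades count as poor.
- **Section 7.1.4** (item 9) collects the full score: "Record the Modified Rankin Scale (mRS) score at 3 months after stroke".

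No section classes grade 3 as good or poor, or says that such patients are left out of the analysis.

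**The concern.** The primary logistic and ROC analyses need a yes/no outcome for every analysed patient, and the plan does not supply one for a patient who scores 3. Two analysts following the text could report different denominators, event counts, odds ratios and AUCs from the same data.

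The literal reading, good against poor with grade 3 set aside, has a further problem. The stated aim is to predict prognosis from early blood samples, when the 3-month grade is unknown. Removing patients because they turn out to be grade 3 leaves a comparison of the two ends of the scale, and performance measured there does not carry over to all AIS patients.

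An open definition also allows the choice to be made after the results are visible. Section 7.3 marks measures to reduce bias as not applicable, and nothing else in the plan prevents this. Finally, the 40% event rate in 5.3 cannot be checked until its mRS range is known.

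**Working it through.** **1. Side-by-side reading.** Three codings are possible:

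- **A:** 0-2 versus 3-6. Keeps the written meaning of good, contradicts the written meaning of poor.
- **B:** 0-3 versus 4-6. Keeps poor, contradicts good.
- **C:** 0-2 versus 4-6, grade 3 dropped. Keeps both, but needs an exclusion that is stated nowhere.

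**2. The plan's own figure.** For a continuous covariate, the standard logistic-regression formula is N = (z₀.₉₇₅ + z₀.₈₀)² / [P(1−P)(ln OR)²(1−R²)]. With P = 0.40 and OR = 2.0 from 5.3, two-sided 5% and 80% power, this is 7.849 / (0.24 × 0.4805) = 68.07 before adjustment. Reading the correlation of 0.5 as R (R² = 0.25) gives 68.07 / 0.75 = 90.8, so 91. Reading it as R² = 0.5 gives 137. Neither is the stated 182 (which is 2 × 91). That is a separate matter; the point here does not depend on it.

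**3. Counts.** The share of grade 3 is not in the documents; 10-20% is assumed. Total n = 182. Under C, n = 182 × (1 − share), that is 163.8 or 145.6. Poor counts are 182 times the relevant proportion, for example 182 × 0.40 = 72.8 and 182 × (0.40 − 0.20) = 36.4.

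**4. Effect on OR and AUC.** Model: marker x standard normal, logit P(mRS ≥ k | x) = aₖ + ln(2)·x, with a₃ and a₄ set to match the outcome proportions. The population logistic fit was computed for each coding, together with the expected unadjusted z at 182 enrolled. A and B return OR 2.00 and AUC 0.68 throughout.

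| 40% means | Grade-3 share | A: n, poor | B: n, poor | C: n, poor | OR under C | AUC under C | Expected z, A / B / C |
|---|---|---|---|---|---|---|---|
| mRS 3-6 | 10% | 182, 73 | 182, 55 | 164, 55 | 2.15 | 0.697 | 3.95 / 3.75 / 3.94 |
| mRS 3-6 | 20% | 182, 73 | 182, 36 | 146, 36 | 2.32 | 0.715 | 3.95 / 3.35 / 3.73 |
| mRS 4-6 | 10% | 182, 91 | 182, 73 | 164, 73 | 2.15 | 0.696 | 4.02 / 3.95 / 4.10 |
| mRS 4-6 | 20% | 182, 109 | 182, 73 | 146, 73 | 2.30 | 0.713 | 3.95 / 3.95 / 4.16 |

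**5. Power.** 80% power needs an expected z of 1.96 + 0.84 = 2.80. The lowest value, 3.35 for B, becomes 3.35 × √0.75 = 2.90 after adjustment with R² = 0.25. Only if the correlation is read as R² = 0.5 does it fall short (3.35 × √0.5 = 2.37).

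**6. Choosing the coding after the fact.** In 200,000 simulated data sets per setting, with n = 182 and no association, each coding alone rejected in 4.9-5.1% at |z| > 1.96. At least one of the three rejected in 8.1%, 8.7% and 9.2% (40% = mRS 3-6; grade-3 share 10%, 15%, 20%) and in 7.8%, 8.4% and 8.9% (40% = mRS 4-6). These rates are for one marker.

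**The case against.** The three codings are not equally supported. C follows the rule as written, while A and B each override half of it. If favorable in 9.1 means good in 7.4, the primary endpoint is 0-2 against the rest, which is A. The upper range may also be a slip for 3-6. These are reasonable readings, but they point in different directions. Favorable is never equated with 0-2, 5.3 is framed in terms of poor prognosis, and nothing in the documents confirms a slip.

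The numerical effects are modest and depend on assumptions. At a 5% grade-3 share, the odds ratio under C is about 2.07 and the error from choosing among codings about 7%. The 95% interval for an odds ratio of 2.0 at z = 3.95 is exp(0.693 ± 1.96 × 0.693/3.95), about 1.4 to 2.8, so the shift under C is well within sampling error. Section 5.3 speaks of high expression, which could mean a dichotomised marker and not an effect per SD. The error inflation arises only if someone tries the codings and reports the best, and nothing shows that this is intended. All of that stands.

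The study is non-interventional and records the full mRS, so every coding can be recovered later. That makes the repair cheap, but it does not define the outcome.

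**Conclusion.** The point holds and must be fixed. The primary binary outcome cannot be derived from the plan for patients with mRS 3. That follows from the text alone and needs no assumption.

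Its size depends on an assumed grade-3 share of 10-20%. On that assumption, codings A and B differ by 18 to 36 poor outcomes out of 182, and C removes the same number of patients. The shifts in odds ratio and AUC also assume proportional odds and 2.0 per SD; they are a moderate upward bias for prediction in all AIS patients. The false-positive rate of 7.8-9.2% applies only if the coding is picked after results are seen.

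No loss of power is claimed. Under C the larger odds ratio largely offsets the smaller sample, and under B the expected z stays adequate when the stated correlation is read as R = 0.5. Mortality, hemorrhagic transformation and progressive stroke do not use the good/poor split and are unaffected.

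**What to change.** Before any outcome data are examined:

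1. In 7.4, assign grade 3. The simplest wording is mRS 0-2 = favorable, mRS 3-6 = poor (not favorable), which keeps the written meaning of good. If 0-3 versus 4-6 was intended, say so and change the definition of good to match.
2. In 9.1 and 10.2, name that one variable as the primary outcome for every AIS patient with a 3-month mRS.
3. In 5.3, state that the 40% refers to the same mRS range, or restate the rate to fit.

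The cost is one line in 7.4, a cross-reference in 9.1 and 10.2, and one clause in 5.3. No new data are needed, because the 3-month mRS is already scheduled. Patients with no 3-month score, for whom 8.3 says only that "patients who were not followed up on time were contacted by telephone", are a separate missing-data question that this change does not settle.

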7.5 Research Intervention Commitment

not applicable

7.6 Research Plan

Visit	Screening period	Observation period					Follow-up period
		1 day after onset	On admission	24 hours after onset	24 hours after onset	7 days after onset	
Informed consent	×						
Inclusion/Exclusion Criteria	×						
Basic information collection	×						
Peripheral venous blood collection		×		×	×	×	
NIHSS score		×		×	×	×	
blood sugar		×					
KLK10, sTREM2 and GFAP detection		×		×	×	×	
MRI						×	
CT	×					×	
mRS score							×

8. Discontinuation of study intervention and discontinuation/withdrawal of study subjects

8.1 Discontinuation of Study Intervention

not applicable

8.2 Discontinuation/Withdrawal of Study Subjects

not applicable

8.3 Loss to follow-up

To reduce loss of follow-up and missing data, patients who were not followed up on time were contacted by telephone.

9. Study endpoint evaluation

9.1 Primary Endpoint Evaluation

The study examines the association between plasma levels of KLK10, sTREM2, and GFAP with favorable functional outcomes at 3 months after stroke onset.

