5.1 Overall Design

A total of 182 patients with first-ever anterior circulation AIS (Acute Ischemic Stroke) hospitalized in the Neurology Department at the Northern Campus of our hospital will be selected as the observation group, and 91 healthy individuals undergoing physical examination will be selected as the control group. For AIS patients, 10 ml of elbow venous blood will be collected at admission and then at 24 hours and 7 days after stroke onset. For healthy individuals, 10 ml of fasting elbow venous blood will

be collected once. The dynamic changes and differential expression characteristics of a group of neuroinflammatory molecules, including KLK10, sTREM2, and GFAP in plasma will be observed. The early changes (at admission and 24 hours after onset) of these neuroinflammatory molecules in plasma will be compared and analyzed in relation to the severity of acute neurological deficits (NIHSS score), infarct volume, brain edema, hemorrhagic transformation, occurrence of progressive stroke, and clinical prognosis at 3 months (mRS score), to evaluate the predictive value of these molecules for clinical outcomes after AIS.

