10.1 General Methods

For descriptive statistical analysis, measurement data conforming to a normal distribution are expressed as mean \pm standard deviation; measurement data not conforming to a normal distribution are expressed as median (interquartile range); count data are expressed as rates or proportions. For comparing two groups of measurement data with normal distribution and equal variance, an independent two-sample t-test is used; for comparing two groups of measurement data not conforming to normal distribution and equal variance, a non-parametric Mann-Whitney U test is used. For count data in contingency tables, Pearson's chi-square test is used if conditions are met; otherwise, Pearson's chi-square test with continuity correction or Fisher's exact test is applied. All tests are two-tailed, with $P < 0.05$ considered statistically significant.

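### The primary endpoint gives three markers equal standing at P < 0.05, with two early draws and no primary test, so the chance of a false-positive primary finding is roughly 11–26% rather than 5%

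*Combined protocol and SAP*

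**What the plan says.** - **Primary endpoint (9.1).** "The study examines the association between plasma levels of KLK10, sTREM2, and GFAP with favorable functional outcomes at 3 months after stroke onset". The three markers stand side by side, and no draw is given.
- **Primary analysis (10.2).** "Univariate and multivariate logistic regression models are used to evaluate independent predictors", with odds ratios, confidence intervals and ROC curves. This covers all three markers and again names no draw.
- **Draws (7.1.4 and 5.1).** 7.1.4 reads "Measure levels of neuroinflammatory markers KLK10, sTREM2, and GFAP in plasma at admission, and at 24 hours and 7 days after stroke". 5.1 narrows the predictive question to the first two: "The early changes (at admission and 24 hours after onset) of these neuroinflammatory molecules in plasma will be compared and analyzed".
- **Significance rule (10.1).** "All tests are two-tailed, with $P < 0.05$ considered statistically significant". No adjustment or testing order is stated there or elsewhere.
- **Sample size (5.3).** One marker and one test, "with an OR of 2.0 for high KLK10 expression", at significance level 0.05 and power 0.8.
- **Hypothesis (2.2) and expected outcome (2.3).** 2.2 argues that single molecules predict too poorly and that a set may do better. 2.3 asks whether early levels of KLK10 and other molecules can serve as prognostic markers.

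**The concern.** The plan has the form of a formal test: a primary endpoint, a powered sample size and a 0.05 threshold. It does not say which test decides. The error rates in 5.3 describe one KLK10 test, whereas 9.1 and 10.2 describe at least three tests of equal standing, and more if both early draws are analysed.

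Nothing written prevents a significant result for one marker at one draw from being reported as meeting the primary endpoint. A claim reached that way does not carry the 5% error rate that 10.1 implies. The choice of marker and draw could also be made after the results are seen.

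**Working it through.** **Inputs from the documents.** Two-sided 0.05 per test (10.1); three markers (9.1, 10.2); two early draws (5.1). **Assumed.** The correlation between test statistics, for which the documents give no figure.

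**The plan's own figure.** The documents state no overall error rate. The nearest figure is the 182 patients in 5.3, which rests on a single test. The usual logistic-regression formula for a continuous covariate, with event rate 0.40, OR 2.0 and R² = 0.5² = 0.25, gives

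(1.960 + 0.842)² / [0.40 × 0.60 × (ln 2)² × 0.75] = 90.8, so 91.

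This does not reproduce 182 as a total; 182 is twice the unrounded value (2 × 90.76 = 181.5). That is a separate question and does not affect this point. What matters here is that 5.3 allows for one test.

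**Step 1: count the tests.**
- One early value per marker: 3 × 1 = 3.
- Each marker at each early draw: 3 × 2 = 6.

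**Step 2: independent tests.** The chance of at least one P < 0.05 when no marker is related to outcome is 1 − 0.95^m.
- m = 3: 1 − 0.8574 = 14.3%.
- m = 6: 1 − 0.7351 = 26.5%.

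**Step 3: correlated tests.** One million sets of correlated normal statistics were simulated under the same null, counting sets with any |z| > 1.96. The simulation error is about √(0.2 × 0.8 / 1,000,000) = 0.0004.

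| Common correlation | 3 tests | 6 tests |
|---|---|---|
| 0 (exact) | 14.3% | 26.5% |
| 0.3 | 13.6% | 24.1% |
| 0.5 | 12.6% | 20.8% |
| 0.7 | 10.9% | 16.4% |
| 0.8 | 9.8% | 13.9% |
| 0.9 | not run | 10.8% |

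**Step 4: nearly identical draws.** If the markers are independent and each marker's two draws correlate at 0.99, six tests give 16.0%, close to the three-test figure of 14.3%. The excess over 5% therefore does not depend on counting two draws.

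**Step 5: one designated test.** One named marker, draw, scale and model, or one joint test, gives 5%.

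**The case against.** **The six tests are inferred.** This stands. 10.2 lists no marker-by-draw tests, and the phrase in 5.1, "The early changes (at admission and 24 hours after onset) of these neuroinflammatory molecules in plasma", could mean one early quantity per marker. That is why three tests are shown beside six. Three tests still give about 11–14% at correlations from 0.7 to 0.

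**The draws may nearly coincide.** 6.1 admits patients up to 24 hours after onset, so for late arrivals the admission and 24-hour samples can be almost the same. This lowers the six-test figure towards the three-test figure, but not to 5%.

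**The multivariate model or the panel idea already covers it.** 2.2 does frame a marker-set hypothesis. However, 10.2 uses the models to look for independent predictors, which gives a P value per marker. No joint test is specified.

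**KLK10 is plainly the lead marker.** The title and 5.3 suggest so, but 9.1 and 10.2 do not say it. The informal priority is a good reason to make it formal.

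**This is an observational biomarker study.** Whether to adjust across distinct markers is partly convention. But the plan does not call itself exploratory: section 4 sets out to determine whether the markers predict prognosis, and 2.1 speaks of confirming it.

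**Stronger readings that the documents do not support.** A reader might infer nine tests by adding the 7-day draw (37.0% if independent). But 5.1 defines early as admission and 24 hours, and the objectives in 1.1 and section 4, the hypothesis in 2.2 and the expected outcome in 2.3 all concern early levels. A reader might also infer that the plan adopts the rule that any significant marker is a success. It states no success rule at all; the percentages price the most liberal rule that it leaves open.

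**Conclusion.** The point holds. The primary endpoint has three co-equal markers and an unspecified early draw, each test is judged at 0.05, and the study is sized for one KLK10 test. If any significant marker counts as success, the false-positive chance when no marker is related to outcome is about 11–14% for three tests and about 11–26% for six. Both ranges depend on assumed correlations, and 11% is not a floor: three tests at correlation 0.8 give 9.8%. What is certain is that the plan does not hold its primary conclusion at the stated 5%.

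A reader might go further and conclude that KLK10 at admission, on a log scale, is the natural primary predictor. The documents do not settle that. Admission can fall anywhere from 0 to 24 hours after onset (6.1), whereas the 24-hour draw is anchored to onset, and 2.1 says blood inflammatory markers keep rising over that period. 5.3 refers to high KLK10 expression, and no section mentions a log scale.

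This should be corrected before marker data are analysed. The data stay usable either way; what is at stake is how a positive headline result can be read.

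**What to change.** Before marker data are analysed, amend 9.1 and 10.2 as follows:

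1. Name one primary test at two-sided 0.05: KLK10, the marker used in 5.3, at one early draw and on one scale. The sponsor should choose and justify the draw and the scale. Because 10.2 runs both univariate and multivariate models, say which one supplies this test.
2. Make the remaining marker-by-early-draw predictors secondary (6 − 1 = 5), with Holm-adjusted P values. The smallest of the five is then compared with 0.05 / 5 = 0.01.
3. Keep the 7-day level for describing the time course only.
4. Alternatively, if the marker-set hypothesis in 2.2 is meant to decide the study, specify one joint test of the three markers at one named early draw as the primary test.

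**Cost.** The change is wording only; no patient procedure or sample changes. A positive result for another marker or draw becomes secondary and needs a smaller P value. With the joint test, the power stated in 5.3 for KLK10 alone would no longer apply directly.

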9.2 Secondary Endpoint Evaluation

- 1) Investigate the correlation between plasma KLK10, sTREM2, and GFAP levels and mortality at 3 months after stroke onset.
- 2) Examine the correlation between plasma KLK10, sTREM2, and GFAP levels and hemorrhagic transformation after infarction, based on brain CT scans to evaluate hemorrhagic transformation of cerebral infarction within 7 days after stroke onset.
- 3) Explore the association between plasma KLK10, sTREM2, and GFAP levels and the occurrence of progressive stroke, with neurological deficits assessed using the NIHSS score. Progressive stroke is diagnosed if the NIHSS score increases by 2 points within 7 days after stroke onset.

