2.1 Research Significance

Stroke is the leading cause of death and disability in China. Intravenous thrombolysis or thrombectomy are currently the only approved early treatments for AIS (acute ischemic stroke). However, due to the limited time window, the number of patients benefiting from these treatments is restricted, leaving many patients with cerebral infarction. Studies have shown that neuroinflammatory molecules rapidly activate post-infarction and are involved in the pathogenesis of cerebral infarction. Moderate inflammation helps clear necrotic tissue and plays a crucial role in tissue repair and remodeling, while excessive inflammation can exacerbate ischemic neuronal damage and impair recovery (*Lancet Neurol*, 2019, 18(11): 1058-1066). Inflammatory markers in the blood rise quickly after 2 hours of stroke onset and continue to increase within 24 hours (*Stroke*.2022;53(7):2249-2259), making early detection of blood neuroinflammatory markers significant for predicting clinical outcomes in AIS. This study aims to dynamically measure changes in a set of neuroinflammatory molecules in the plasma, including KLK10, and analyze their correlation with the severity of acute neurological deficits, infarct volume, brain edema, hemorrhagic transformation, progressive stroke, and clinical outcomes at three months. Given the time-sensitive and challenging nature of AIS management, confirming that a set of neuroinflammatory molecules like KLK10 can accurately predict post-stroke clinical outcomes would have significant scientific value for guiding early treatment of AIS and could provide new molecular targets for stroke prevention and treatment.

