6.1 Inclusion Criteria

Inclusion criteria for AIS patients:

- Selection of 182 patients with first-ever acute ischemic stroke (AIS) who are hospitalized at our hospital, aged ≥ 18 years, with no restriction on gender;
- Patients must be admitted within 24 hours of the onset of AIS;
- Diagnosis must be confirmed by cranial magnetic resonance imaging (MRI) or computed tomography (CT);
- All enrolled patients must provide written informed consent.

Inclusion criteria for healthy controls:

- Age and gender matched;
- No organic diseases;
- Written informed consent must be signed

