6.2 Exclusion criteria

- Intracranial hemorrhage;
- Pregnancy;
- Stroke with unknown onset time;
- Malignant tumors;
- Hematologic disorders;
- Severe liver or kidney dysfunction;
- Recent myocardial infarction (less than 3 months);
- Ongoing anti-inflammatory drug treatment

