10.3 Analysis of Secondary Study Endpoints

- 1) The correlation between plasma KLK10, sTREM2, and GFAP levels and hemorrhagic transformation and mortality at 3 months was investigated: univariate and multivariate logistic regression models were used to evaluate independent predictors, and ORs and 95% CIs were calculated. ROC curves were drawn and AUCs were calculated.
- 2) The association between plasma KLK10, sTREM2 and GFAP levels and the occurrence of progressive stroke was studied: univariate and multivariate logistic regression models were used to evaluate independent predictive factors, calculate OR and 95%CI. ROC curves were drawn and AUC was calculated.

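### Progressive stroke is timed from onset but can only be scored from admission, up to 24 h later; the recorded rate, and the admission-marker OR and AUC, can therefore depend on arrival time

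*Combined protocol and SAP*

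**What the plan says.** All references are to the combined protocol and SAP.

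- Section 9.2 (Secondary Endpoint Evaluation): "Progressive stroke is diagnosed if the NIHSS score increases by 2 points within 7 days after stroke onset". The score against which the rise is measured is not given.
- Section 6.1 (Inclusion Criteria): "Patients must be admitted within 24 hours of the onset of AIS".
- Section 7.1.4 schedules the NIHSS "at admission, and at 24 hours, 4 days, 7 days, and discharge after stroke". No score exists before admission.
- Section 5.1 names the predictors: "The early changes (at admission and 24 hours after onset) of these neuroinflammatory molecules in plasma". One of the two early samples is therefore tied to arrival and the other to a fixed time after onset.
- Section 2.1, on timing: "Inflammatory markers in the blood rise quickly after 2 hours of stroke onset and continue to increase within 24 hours".
- Section 10.3 plans univariate and multivariate logistic models, with ROC curves, for progressive stroke. It lists no covariates, and time from onset to admission is not mentioned as an adjustment anywhere.
- Section 6.2 excludes "Stroke with unknown onset time", so onset-to-admission time can be derived for every patient.

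**The concern.** The outcome window opens before anything can be measured. A patient who worsens at 10 h and arrives at 20 h carries that worsening in the admission score and is recorded as not progressing. The same patient arriving at 3 h would be recorded as an event. For someone arriving close to 24 h, the admission and 24-h scores almost coincide, which leaves in effect two later assessments by day 7 (4 and 7 days) instead of three.

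Two things follow. First, the reported 7-day rate is too low whenever any progression precedes admission, and by how much depends on when patients arrive. Second, late arrivals have less chance of a recorded event. If they also have higher admission levels because the marker has had longer to rise, arrival time is linked to both predictor and recorded outcome. That pulls the admission-marker OR downward and distorts its AUC. The univariate OR and a single-marker ROC curve contain nothing that could correct for it.

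**Working it through.** **Is there a plan figure to reproduce?** No. The documents give no rate, timing or power for progressive stroke. The 182 patients in section 5.3 were calculated for 3-month prognosis and do not bear on this point.

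**Step 1: observable window (documents only).** The window is 7 × 24 = 168 h. Arrival at time t leaves 168 − t hours, so arrival at 24 h leaves 144 h. The largest loss is 24/168 = 14.3%.

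**Step 2: events that cannot be seen (assumptions).** The documents give neither event timing nor arrival mix. Assume arrival uniform over 1 to 24 h (mean 12.5 h), true 7-day progression 25%, and a share f of events spread evenly over the first 24 h. The unseen share for arrival at t is f × t/24, and its mean is f × 12.5/24. The observed rate is 25% × (1 − mean unseen share). Constant hazard gives f = 24/168 = 14.3%.

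| f | unseen, arrival 3 h | unseen, arrival 23 h | mean unseen | observed rate |
|---|---|---|---|---|
| 14.3% | 1.8% | 13.7% | 7.4% | 23.1% |
| 20% | 2.5% | 19.2% | 10.4% | 22.4% |
| 33% | 4.1% | 31.6% | 17.2% | 20.7% |
| 50% | 6.3% | 47.9% | 26.0% | 18.5% |

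With 182 patients there would be 182 × 0.25 = 45.5 true events. About 45.5 × 0.074 = 3.4 are unseen at constant hazard, and 45.5 × 0.26 = 11.8 at f = 50%. If arrivals are earlier (mean 9 h), a mean loss of 10% needs f = 0.10 × 24/9, about 27%.

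**Step 3: admission-marker OR (simulation).** The marker is r × (standardised arrival time) + √(1 − r²) × biology, with r = 0.5. Progression depends on biology only, and events count only if they occur after arrival. ORs are per SD.

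- No true association, unadjusted: about 0.97 at constant hazard, 0.96 at f = 20%, 0.93 at f = 33% and 0.89 at f = 50%. At n = 182 the two-sided 5% test rejects about 5% to 10% of the time across f = 20% to 50%. Adding onset-to-admission hours returns the OR to about 1.00.
- True OR 1.6, unadjusted, n = 182: 1.51 with no hidden events, then 1.43, 1.37 and 1.29 at f = 20%, 33% and 50%. Power goes from 64% to 49%, 38% and 25%.
- Weaker time dependence (r = 0.3), true OR 1.6: 1.57 with no hidden events, then 1.50, 1.46 and 1.40.
- Earlier arrivals (exponential, mean 8 h, capped at 24 h; marker shifting 0.5 SD per SD of arrival time), no true association: 0.98, 0.95 and 0.91 at f = 14%, 30% and 50%.

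**Step 4: the 24-h marker.** Its level does not depend on arrival. The null OR stays at about 1.00. A true OR of 1.6 reads about 1.55 to 1.57, and a true OR of 2.0 reads about 1.95, 1.92 and 1.86 at f = 14%, 30% and 50%. Adjusting for arrival time changes almost nothing.

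**Step 5: what the covariate does and does not do.** With no hidden events at all, adding arrival time already raised power for the admission marker from 60% to 74% in a separate run, because it removes timing noise from the marker. Adjusted power in that run still fell to 67%, 64% and 57% at f = 20%, 33% and 50%. The covariate removes confounding; it does not recover unseen events.

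**The case against.** The strongest reply is that worsening before hospital cannot be scored in any admission cohort, that this is a secondary endpoint, and that every driver of the size is assumed. Much of that stands. Section 2.1 speaks of inflammatory markers in general, and the documents give no hour-by-hour plasma data for KLK10, sTREM2 or GFAP. At constant hazard the loss is modest. Section 10.3 leaves its covariates open, so adjustment for arrival time is unstated, not ruled out. None of this removes the structural point: the window as worded cannot be observed in full, the reference score is missing, and the univariate results cannot be adjusted.

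Three stronger readings are tempting, and the documents do not support them.

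- A reader might infer that all the marker ORs for progressive stroke are biased by arrival time. Section 5.1 also uses a sample at a fixed 24 h after onset, and that marker keeps a null OR of about 1.00.
- A reader might extend the point to hemorrhagic transformation, which is also counted over 7 days from onset. That outcome is read from CT and is not a rise over a baseline score. Under section 6.2, intracranial hemorrhage at entry removes the patient from the cohort; the patient is not miscounted as event-free. That is eligibility selection, a different mechanism, and nothing here quantifies it.
- A reader might credit all the power regained by adjustment to repaired ascertainment. Part of it is the removal of timing noise from the marker.

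**Conclusion.** The point holds for progressive stroke and, for associations, for the admission sample. That the window opens before the first score, and that no reference score is named, follows from the documents alone. Under-counting occurs whenever any progression precedes admission, whether or not the marker varies with arrival.

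Confounding of the admission-marker OR and AUC is conditional: it needs some progression before arrival and a marker level that changes with time since onset. With uniform arrival, 25% progression and marker-time correlation 0.5, roughly 7% to 26% of events are unseen and a null OR reads about 0.97 to 0.89. The distortion is smaller with earlier arrivals or weaker time dependence. The 3-month primary endpoint does not depend on this window and is unaffected. This is an inexpensive improvement worth making, not a fault that undermines the study.

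**What to change.** 1. In section 9.2, define progressive stroke as a rise of at least 2 points over the admission NIHSS, observed from admission to day 7 after onset, and label the reported rate that way.
2. In section 10.3, prespecify hours from onset to admission as a covariate in the admission-marker models for progressive stroke. The 24-h-marker models do not need it for this reason.
3. Add one sensitivity analysis on a window common to all patients: a rise over the 24-h NIHSS by day 7.

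Cost: a change of wording, one model degree of freedom, and fewer events in the sensitivity analysis. No new visit, sample or data item is needed, because onset time is known for every eligible patient and admission time is already required to apply the 24-h entry rule. Events before arrival remain unseen, which is why the rate should be labelled as running from admission.
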